4.3. Biosafety: N/A

4.4. Stem Cells: N/A

5. Procedures Involved

[figure not shown]
5.1. Study Design:

The RCT among 368 eligible melanoma survivors will be conducted in two Waves (two consecutive summers), with planned adjustments to improve recruitment, compliance and participant retention between study Waves, see Figure 3. Wave 1 may enroll up to 184 participants, though given logistical constraints due to working from home during the pandemic, fewer may be recruited, with the plan to obtain the full 368 by the end of Wave 2.

Figure 3. Phase 2 Study Design.

PROTOCOL TITLE: Wearable device intervention to improve sun behaviors in melanoma survivors

VERSION DATE: 07/19/2021

5.2. Study Procedures –Randomized Controlled Trial:

Randomization. Following written consent and completion of the baseline survey, participants will be randomized with a 1:1 ratio to the intervention or control arm. Randomization will be stratified by age (<50 years, 50+ years), gender, years since melanoma diagnosis (<2 years, 2-5 years, 6-9 years) and highest melanoma stage (I, II, III/IV). We will use block randomization with random blocks of size 2 and 4 to improve balance. The staff recruiting and enrolling participants will be blinded to their randomization. The study statistician will use R to generate random sequence numbers based on the stratified, block randomization scheme and upload the allocation list to REDCap. Following consent and screening, the study coordinator at the University of Minnesota will randomize participants.

Study Initiation. Following randomization, participants will then be mailed their device in early summer (with appropriate version of the mobile app based on randomization) and study assigned log-in information. This will include a study-created user name to be used with the device/mobile app to allow for direct retrieval of the device-collected data by the study coordinator. Participants will also be provided written training materials. Participants will be provided with a study phone number and email to contact the study coordinator with any remaining technical issues or questions.

PROTOCOL TITLE: Wearable device intervention to improve sun behaviors in melanoma survivors

VERSION DATE: 07/19/2021

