Study Procedures. Users will be asked to wear the devices and sync it with the mobile app every day for 12 weeks, regardless of planned physical or outdoor activities. The study coordinator will view the data of all participants (both intervention and control) weekly to monitor device use. The study coordinator will contact participants who do not use their device more than 3 days in any given week to determine barriers and encourage use. Participants will be asked to complete periodic surveys and return the device via mail at the end of the intervention period.

Data Collection. Study measures will be collected via online surveys (in REDCap ³³) and the Shade device. The survey will be accessible anywhere with an internet connection, see section 6.0. Self-administered questionnaire data will be collected at the start of the intervention (week 0), week 4, week 8 and week 12 (end of intervention), and week 64 (1 year after the end of the intervention; the end of the following summer). After completing the surveys, participants will be directed to the study website. Survey measures and their purpose are detailed in Table 2.

Table 2. Study Measures.				Weeks				
Measure	Purpose	Description	# Items	0	4	8	12	64
Health behaviors	Distraction	Measures of healthy behaviors, including alcohol, smoking, fruits, vegetables, vitamin D, height, weight	10	X	X	X	X	X
Physical activity	Secondary outcome (unintended consequence)	Strenuous, moderate and mild activity times per week and amount of time per session	6	X	X	X	X	X
Sun Protection Habits	Primary outcome	Use of sunscreen, hat, shirt and shade while in the sun; Likert scale	14	X*	X*	X*	X*	X*
Sunburns	Secondary outcome (efficacy)	How many times did you have a red OR painful sunburn that lasted a day or more?	1	X**	X*	X*	X*,**	X**
Sun Exposure and other Protection measures	Validation/Comparison with device data	Exposure during weekday and weekend days, sunscreen details, indoor tanning	11	X**	X*	X*	X*	X**

PROTOCOL TITLE: Wearable device intervention to improve sun behaviors in melanoma survivors

VERSION DATE: 07/19/2021

Beliefs, Intentions, Self-Efficacy regarding sun protection behaviors	Substudy (if intervention fails)	Reasoned Action Battery: Intention, Attitude, Behavioral beliefs, Normative pressure, Normative beliefs, Self-efficacy	84	X			X (60)	X (60)
Sun protection knowledge	Secondary outcome (efficacy)	Knowledge of sun protection (items covered in brochure)	6	X			X	X

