10.1. Local Number of Participants to be Consented as Eligible for Recruitment (Verbal): 460

Local Number of Participants to be Consented to Full Study (Written): 390

11. Local Recruitment Methods

11.1. Recruitment Process:

Trained and experienced staff of HealthPartners Institute Center for Evaluation and Survey Research (CESR) will oversee the recruitment process. The CESR has been engaged in research both within the HealthPartners patient/member population and broader community for more than 15 years and is directed by a seasoned PhD survey methodologist and health services researcher, who oversees staff of

PROTOCOL TITLE: Wearable device intervention to improve sun behaviors in melanoma survivors

VERSION DATE: 07/19/2021

bachelors and masters-level employees with experience and training in survey, interview, chart-audit, and electronic data capture for research purposes. The CESR employs REDCap (Research Electronic Data Capture)³³ as a primary data capture and management platform.

To recruit the required sample size and ensure meaningful measures of protection sun exposure, participants will be enrolled in two cohorts (Wave 1 and 2) over two consecutive summers. Recruitment will occur in the spring with the study intervention running over the summer both years to account for seasonality.

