Statistical analysis will focus on evaluating the efficacy, unintended consequences and implementation of the intervention in this RCT. The main analysis of the primary outcome (self-reported overall sun protection score) will be a two-sample two-sided two-sample t-test comparing scores at the end of the intervention period (12 weeks) between intervention and control groups. Randomization should result in two groups that are similar for patient characteristics and other extraneous factors that may influence sun exposure and protection behaviors, however, we will compare the randomized groups by Wave, gender, age, stage of disease, device use (low/high), and baseline measures of sun protection and exposure behaviors using two-sample t-tests and Chi-squared tests to identify potential confounding factors which may not be balanced between the two groups. We will supplement the primary analysis with a multivariate linear regression model to account for any identified differences at baseline. A secondary analysis will explore changes in the sun protection score over the intervention period (baseline, weeks 4, 8 and 12) using a mixed effects regression model. This analysis will not be completed until both Waves have been conducted.

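### The primary week-12 t-test is valid but ignores the pre-randomization baseline score and the four stratification factors, so it gives up precision that a pre-specified adjusted model would recover at almost no cost

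*Combined protocol and SAP*

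**What the plan says.** Section 15.3 defines the main test as a "two-sample two-sided two-sample t-test comparing scores at the end of the intervention period (12 weeks) between intervention and control groups". No covariate is included.

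Suitable covariates exist before allocation. Section 5.2 states: "Following written consent and completion of the baseline survey, participants will be randomized with a 1:1 ratio to the intervention or control arm". It continues: "Randomization will be stratified by age (<50 years, 50+ years), gender, years since melanoma diagnosis", with highest stage as the fourth factor. The data collection paragraph of the same section says "Self-administered questionnaire data will be collected at the start of the intervention (week 0), week 4, week 8 and week 12", and Table 2 marks the sun protection habits items at week 0 with a four-week recall period.

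Elsewhere in section 15.3 the baseline score appears only outside the primary test:
- The plan will "compare the randomized groups by Wave, gender, age, stage of disease, device use (low/high), and baseline measures of sun protection" and exposure behaviors, by t-tests and Chi-squared tests. Then: "We will supplement the primary analysis with a multivariate linear regression model to account for any identified differences at baseline".
- A secondary analysis explores "changes in the sun protection score over the intervention period (baseline, weeks 4, 8 and 12) using a mixed effects regression model".
- Paired t-tests compare baseline with post-intervention scores within each arm.
- The multiple imputation model will contain baseline variables that are not named.

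**The concern.** A baseline measure of the outcome often explains part of the outcome's variance. Leaving it out leaves that variance in the standard error, so the primary confidence interval is wider than it needs to be. Stratified allocation balances the strata between arms, but a t-test does not credit that balance. To the extent that the strata predict the score, its standard error is somewhat too large.

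The supplementary regression does not reliably make this good, for three reasons.
- Its covariates depend on observed imbalance, which says nothing about whether a variable predicts the outcome.
- Its list includes device use, which is measured after randomization. Device use may respond to assignment, since only the intervention app sends limit notifications (section 4.1).
- Its list omits years since diagnosis, a stratification factor.

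**Working it through.** **Inputs.** From the documents: 368 randomized 1:1 (sections 5.1, 5.2); 85% complete week 12, stated as 314 with outcome data; effect size 0.40; two-sided alpha 0.05; stated power 95% (section 15.2). Assumed, because the documents do not give them: the baseline to week-12 correlation r, the variance share explained by the strata, and 0.30 SD as an example of a smaller effect. Low values of r are included because "Recruitment will occur in the spring with the study intervention running over the summer both years to account for seasonality", so the four-week recall at week 0 may cover a different season from that at week 12.

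**The plan's own figure.** With 157 per arm and d = 0.40, power is 94.3% by the normal approximation and 94.2% by the noncentral t, so the stated 95% is reproduced to within a point. Since 368 × 0.85 = 312.8, the rest uses 313 completers (156 and 157). Using 314 changes power by less than 0.2 points.

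**Unadjusted test.** SE = √(1/156 + 1/157) = 0.113 SD. The 95% half-width is 1.968 × 0.113 = 0.222 SD. Power is 94.1% at d = 0.40 and 75.4% at d = 0.30.

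**Adding the baseline score.** The residual SD is multiplied by √(1 − r²), so the half-width is 0.222 × √(1 − r²) and the effective standardized effect is d/√(1 − r²). The equivalent number of unadjusted completers is 313/(1 − r²).

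| r | √(1 − r²) | Interval narrower by | Half-width (SD) | Power, d = 0.40 | Power, d = 0.30 | Equivalent completers |
|---|---|---|---|---|---|---|
| 0 | 1.000 | 0% | 0.222 | 94.1% | 75% | 313 |
| 0.2 | 0.980 | 2% | 0.218 | 94.9% | 77% | 326 |
| 0.3 | 0.954 | 5% | 0.212 | 95.9% | 79% | 344 |
| 0.4 | 0.917 | 8% | 0.204 | 97.0% | 82% | 373 |
| 0.5 | 0.866 | 13% | 0.193 | 98.3% | 86% | 417 |
| 0.6 | 0.800 | 20% | 0.178 | 99.3% | 91% | 489 |
| 0.7 | 0.714 | 29% | 0.159 | 99.9% | 96% | 614 |

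**Chance imbalance.** The baseline difference between arms also has SE 0.113 SD, so r × 0.113 carries into the unadjusted estimate: 0.02 SD at r = 0.2 and 0.08 SD at r = 0.7. The t-test interval already reflects this variation.

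**Strata.** If they explain R² of the variance and are fully balanced, the t-test standard error is too large by a factor of at most 1/√(1 − R²). That is about 1%, 2.5% and 5% for R² of 2%, 5% and 10%.

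**Cost of the full model.** Covariates: baseline 1, age 1, gender 1, years since diagnosis 2, stage 2, Wave 1, giving 8 in all. In simulation (4,000 trials per setting, stratified blocks of 2 and 4, random dropout to 313) the interval changed by +0.5% at r = 0, and by −1.6%, −4.1%, −13.0% and −28.2% at r = 0.2, 0.3, 0.5 and 0.7. At r = 0, power at d = 0.40 was 94.0% against 94.2% for the t-test. At d = 0.30, power rose from 75.0% to 78.8% (r = 0.3) and from 75.3% to 86.8% (r = 0.5).

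A cruder formula charges full chance imbalance for every covariate, although stratified allocation removes most of it for the strata. It gives 93.6% at d = 0.40. On the same basis, a model with baseline and strata only (7 covariates, 314 completers) breaks even at R² = 7/(304 + 7) = 2.3%, or r of about 0.15.

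**Type I error.** In a further simulation of the seven-covariate model it was 4.3% to 5.4% for the t-test and 4.9% to 5.7% for the adjusted model (Monte Carlo SE about 0.35 points). Both are close to nominal.

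**The supplementary regression.** No threshold for an identified difference is stated. At an assumed 0.05, randomization would make the baseline score differ in about 5% of trials, so it would be left out of the regression about 95% of the time.

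**The case against.** The strongest reply is that nothing here is an error. The t-test is fixed in advance, the power calculation uses the same test, and planned power is about 94%. At the protocol's own effect size, adjustment adds only about 1 to 4 points for r between 0.2 and 0.5. The range of r is assumed, and the season gap makes low values plausible. The table covers baseline adjustment alone and complete cases, whereas the recommended model has eight covariates and the plan uses multiple imputation. The secondary mixed model also uses the baseline score whatever the balance and, depending on its unstated form, might recover much of the precision.

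Most of this is fair and sets the weight of the point. The size of the gain is uncertain, and the interval under imputation was not computed. But the net simulation figures are close to the table, and the full model's worst case is trivial. A secondary mixed model of unstated form does not narrow the primary interval. The 94% also depends on an effect borrowed from another intervention, while controls here wear the device and receive basic sun-protection information (section 4.1). A smaller true effect is plausible, and that is where the added precision matters most.

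One practical point also stands. The listed strata for years since diagnosis stop at 6-9 years, while eligibility runs from 2010 and this version is dated July 2021. Some participants may have no listed level.

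**Conclusion.** The concern holds as a point of efficiency. The primary test is valid, and slightly conservative to the extent that the strata predict the score. A pre-specified adjusted model would narrow the primary interval by about 2% to 29% for assumed r of 0.2 to 0.7, mostly through the baseline score. The gain in power is small at 0.40 SD and material at 0.30 SD. If the covariates explain nothing, the loss at 0.40 SD is 0.2 to 0.5 power points. These figures assume 313 completers missing at random, a linear baseline relation and a common variance. The change should be made, though no conclusion is invalid without it. That the baseline score and strata are absent from the primary test is certain; how much is gained is not, because r is unknown.

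**What to change.** In section 15.3, make the primary analysis a linear model of the week-12 score on arm, baseline sun protection score, age group, gender, years since diagnosis and stage as main effects, and Wave. Fit it regardless of observed balance. Keep the unadjusted t-test as a supportive analysis. Stop using baseline significance tests to trigger adjustment, and do not adjust for device use. State how diagnoses older than the last listed stratum are coded, and name the same covariates in the imputation model.

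The cost is about one paragraph of text and the amendment that carries it. All covariates are known by the time of randomization, no new data are needed, and the sample size is unchanged.

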Control Group. The control group will be offered both components (device and informational website), however, they will be provided a version of the mobile app that only collects the UVR exposure and does not provide notifications as they reach daily limits or summary information about exposure. The controls will also be provided basic information on sun exposure and protection recommendations as part of the website, however they will not receive the messaging regarding barriers. The attention-control group was chosen over no intervention for a few reasons; one, we

PROTOCOL TITLE: Wearable device intervention to improve sun behaviors in melanoma survivors

VERSION DATE: 07/19/2021

can objectively measure UVR exposure in both groups; two, providing the device to the control group will help with recruitment, engagement and retention.

4.2. Drug/Device Handling:

The proposed research involves the use of a commercially-available environmental tracker for UV exposure. It is not a medical device.

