Process Measures. We will focus on a number of metrics regarding study implementation, including recruitment, compliance/engagement, retention, and satisfaction/usability of the device. Recruitment metrics will include a proportion of eligible individuals who agree to participate and number of contacts required to recruit a participant. Measures of compliance and engagement will focus on device set-up and intervention usage, including time from recruitment to device use, average number of days the device is worn per week, number of times the study coordinator contacted to remind use, and self-reported engagement/response to the UVR notifications on the mobile app. Study retention will be measured as the proportion of participants who complete the baseline and each of the follow-up surveys. Finally, we will measure satisfaction with the device. The implementation metrics will be examined after Wave 1 is complete in order to identify areas of opportunity to improve recruitment, compliance/engagement and retention that can be implemented prior to starting Wave 2. While we will keep the intervention consistent across Waves, we will consider alternative methods of recruitment, incentives, reminders, and other actions to maximize engagement and retention.

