We plan to perform all primary statistical analyses following intention-to-treat (ITT) procedures. That is, all subjects allocated to a treatment or intervention will be followed up, evaluated, and analyzed as members of that group or treatment arm regardless of their compliance with the assigned treatment. While it is not expected that participants will be incorrectly assigned, some may not use the device and certain features. For that reason, we will also summarize device use and consider sensitivity analyses exploring the intervention effect using per-protocol methods (incorporating device use) as opposed to ITT. *A priori*, we anticipate that the amount of use of the intervention will predict sun protection and exposure behaviors, though we will likely be underpowered for this analysis.

Every effort will be made to encourage participants' compliance and data completeness. Nevertheless, we expect some amount of missing data. We plan to perform a comprehensive missing data analysis employing statistical methods that are valid under different missingness assumptions to determine if conclusions are sensitive to missing data. The primary missing data method will be multiple imputation using the Markov Chain Monte Carlo (MI-MCMC) method^{36,37} assuming that data are missing at random—that is, the probability that an observation is missing can depend on the observed data but not on the missing data. We will include appropriate baseline variables into the MCMC procedure to make the conditional independent missing assumption less stringent. If the treatment group is associated with missingness, we will conduct multiple imputation for each treatment group separately³⁸. The MI-MCMC method allows arbitrary missing patterns including intermittent missing and dropout. We will also perform a simple imputation analysis as a sensitivity analysis; specifically, the linear interpolation method will be used for intermittent missing (e.g., when people forget to charge or wear the device), while the last week average value carried forward method will be used for dropouts, assuming that the average of the last 7 days' data will be a good estimate of the missing data.

15.4. Data Integrity:

Data will be entered and stored in REDCap. Data will be reviewed for completeness and cleanliness on an ongoing basis by the study coordinator and statistician.

16. Confidentiality

PROTOCOL TITLE: Wearable device intervention to improve sun behaviors in

melanoma survivors

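### Section 15.3 screens device use, which exists only after randomization, as a potential confounder and does not settle whether it enters the supplementary adjusted model

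*Combined protocol and SAP*

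**What the plan says.** Section 15.3 (Statistical Analysis) makes the main analysis an unadjusted two-sample t-test of the 12-week sun protection score. It then lists variables on which the arms will be compared: Wave, gender, age, "stage of disease, device use (low/high), and baseline measures of sun protection and exposure behaviors". The stated purpose is "to identify potential confounding factors which may not be balanced between the two groups". The next sentence supplements the t-test with a "multivariate linear regression model to account for any identified differences at baseline". It gives no covariate list, no threshold for calling a difference, and no cut-off between low and high use.

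The timing of device use is set elsewhere:

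- Section 5.2, Study Initiation: "Following randomization, participants will then be mailed their device in early summer".
- Section 5.2, Study Procedures: during the 12 weeks the coordinator will "view the data of all participants (both intervention and control) weekly to monitor device use".
- Section 6.2, Process Measures: the engagement metrics include "average number of days the device is worn per week".

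Section 15.3 also gives device use a separate role, in sensitivity analyses using "per-protocol methods (incorporating device use) as opposed to ITT", and says the amount of use is expected to predict the behaviors under study.

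**The concern.** A confounder of a randomized comparison would have to precede assignment. Device use follows it and may be affected by it: under Control Group in section 4.1, the control app "does not provide notifications as they reach daily limits or summary information about exposure". The plan does not say that arm affects use, but a difference is plausible, and the plan itself expects use to go with the outcome. If both hold and use enters the regression, the arm coefficient compares participants with the same level of use. It no longer estimates the effect of assignment.

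The text does not settle entry. The screening list makes device use a candidate, while the phrase about baseline differences can be read to exclude it. The adjusted estimate is there to support the primary result, so the choice of model should not be open once the data are seen.

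**Working it through.** **1. Is device use a baseline variable?** Table 2's item totals answer this.

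- Week 0 without device use: 10 + 6 + 14 + 1 + 11 + 84 + 6 + 14 + 14 + 18 + 5 + 15 = 198, the printed total. The 9 device-use items are not asked.
- Week 4 with device use: 10 + 6 + 14 + 1 + 11 + 9 = 51, the printed total. Without those items it would be 42.

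Device use is therefore measured only after randomization, in line with the mailing date.

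**2. The plan's own figures (context; none is disputed).** 368 × 0.85 = 312.8, against 314 stated. With 157 per arm, effect 0.40 and two-sided 0.05, power is 94.3% (normal) or 94.2% (noncentral t), against 95% stated. The standard error of the unadjusted difference, in SD units, is √(2/157) = 0.113.

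**3. What adjustment would do.** In a linear model of score on arm and high use,

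adjusted effect = unadjusted effect − b × (p_I − p_C),

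where b is the within-arm difference in score between high and low users, and p_I and p_C are the high-use proportions in intervention and control. When b is positive, the estimate falls if intervention use is higher, rises if control use is higher, and does not move if use is equal.

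**4. Illustration.** The documents give no use rates, so these inputs are assumptions: a true effect of 0.40 SD; a latent motivation with correlation 0.6 with the score and g = 0.3 or 0.5 with the tendency to use the device; no effect of use itself on the score; and imbalance flagged at Chi-squared p < 0.05. Then

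b = 0.6 g [φ(z_C) + φ(z_I)] / [p_C(1 − p_C) + p_I(1 − p_I)], with z = Φ⁻¹(p).

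For 60% vs 80% and g = 0.5: b = 0.30 × (0.386 + 0.280) / (0.24 + 0.16) = 0.50. The shift is 0.50 × 0.20 = 0.10, giving 0.30. Simulation (20,000 trials per scenario, 157 per arm) agrees:

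| High use, control vs intervention | Adjusted effect (g = 0.3 to 0.5) | Trials flagged |
|---|---|---|
| 60% vs 60% | 0.40 | 5% |
| 60% vs 70% | 0.37 to 0.35 | 46–47% |
| 60% vs 75% | 0.36 to 0.33 | 81–82% |
| 60% vs 80% | 0.34 to 0.30 | 97–98% |
| 70% vs 60% | 0.43 to 0.45 | 46–47% |
| 75% vs 60% | 0.44 to 0.47 | 81% |

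In flagged trials with unequal use and a true effect of 0.40, the significance verdict differs from the t-test in 5–19% when intervention use is higher and in about 4–7% when control use is higher. With no true effect, false claims of benefit in flagged trials are 0.2–1.3% when intervention use is higher and about 4–10% when control use is higher, against a nominal 2.5%. In the first case the excess errors favor control (about 5–14%).

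**5. If use itself also improves the score.** Assume 50% high use in control, and that high use adds up to 0.5 SD, alone or alongside a shared motivation factor. An unadjusted effect of 0.37 to 0.40 then falls to about 0.22 to 0.34 at 70% intervention use and to about 0.14 to 0.30 at 80%.

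**The case against.** The best reply is that the only sentence governing model entry limits adjustment to baseline differences, and device use cannot be one. Together with the ITT commitment and the separate per-protocol role in section 15.3, this suggests a misplaced item in a list rather than an intention to adjust. That reading is reasonable, and it is why the point is that entry is left open, not that the plan adjusts for use. But the regression is the only use stated for the screen, so on that reading listing device use has no purpose. Nothing tells the analyst to leave it out.

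A second reply is that use may hardly differ by arm. Section 4.1 does not list the morning and evening wear and charging prompts among the features withheld from controls. Section 7.1 says participants can see their own device data in the app, without limiting this to one arm. Weekly monitoring and the lottery (section 11.4) cover everyone. This stands as a reason to expect a smaller difference, and with equal use there is no systematic bias. It does not make device use a legitimate confounder.

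Third, the size depends on assumed inputs, and the 0.10 SD maximum shift in the table belongs to those scenarios only. That also stands: step 5 shows larger shifts under other assumptions.

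**Conclusion.** The concern holds. Device use arises after randomization, is wrongly screened as a potential confounder, and its place in the supplementary model is undecided. The consequence is limited to that adjusted estimate. The size and direction of any distortion depend on which arm uses the device more and on use being positively related to the outcome. In the scenarios without a direct effect of use, the shift is at most 0.10 SD, below one standard error (0.113). It is larger if use itself improves the score: in the most extreme case examined, 0.37 falls to 0.14. This should be corrected before analysis, but it does not threaten the primary result.

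**What to change.** In section 15.3, and in the copy of its text carried in the table of contents:

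- Delete device use (low/high) from the list of variables compared to find confounders, and state that it will not enter the supplementary regression.
- Name the covariates of the adjusted model in advance, all measured before randomization and already collected: for example the baseline sun protection score, Wave, and the stratification factors in section 5.2 (age group, gender, years since diagnosis, highest stage). A closed list also removes the choice after the data are seen.
- Keep the summary of device use by arm as a process measure, which sections 6.2 and 15.3 already provide for, and use the variable analytically only in the per-protocol sensitivity analysis, with the low/high cut-off defined beforehand.

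The cost is wording only: no new data and no additional participants.
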